### Sample Size

Up to Fifteen (15) patients are expected to complete the study at all sites

## 8 RISK ANALYSIS

Risk analysis for The Sinusway device has been conducted as part of FDA 510k submission (K162916). This risk analysis is applicable to the proposed clinical investigation. The potential risks described below will be explained to the subject in the informed consent process.

### 8.1 Potential risks – (Sinusway):

Endoscopy is a minimally invasive, diagnostic medical procedure. Overall, nasal endoscopy is a safe and low risk procedure. Nonetheless, potential complications such as mucosal trauma and bleeding may occur, particularly in susceptible patients with increased risk of bleeding, such as those receiving aspirin or other anticoagulant medications (i.e. Plavix, Coumadin, etc.). In addition, adverse reactions to the topical decongestants or anesthetic provided prior to the procedure may occur.

Since the Sinusway endoscope will be used in conjunction with balloon sinus dilation, the following risks which are associated with BSD and/or endoscopic sinus surgery are presented.

### Risk associated with Endoscopic Sinus Surgery

Surgeons performing routine endoscopic interventions are faced with minor complications in 5% and major complications in 0.5–1% [21]

- Infection- A patient with sinusitis is at risk of developing infection (abscesses, meningitis, etc.) Infection risk increases with the invasiveness of the intervention. The rate of intracranial infections where the intervention is maximized is 1.6% and the rate of infection-related mortality is 0.125%. It is comparable to the one of transcranial surgeries not involving the use of an endoscope [5,6,7]. The Risk of Infection following Sinusway use is mitigated since the Sinusway endoscope is a disposable intended for single use only.
- Bleeding- Bleeding may occur, particularly in susceptible patients with increased risk of bleeding, such as those receiving aspirin or other anticoagulant medications (i.e. Plavix, Coumadin, etc.) [20]. The rate of peri- or postoperative bleeding is around 2% altogether; transfusions were required in about 0.2% of cases [8,9].

- Nasomucosal injury- Nasomucosal injury may occur during transnasal endoscopy. Nasomucosal injury was assessed in 1569 patient that underwent unsedated transnasal esophagogastrroduodenoscopy (EGD), at termination of the procedure. Normal mucosa was observed in 68% of cases, redness of mucosa was observed in 19% of cases, oozing hemorrhage was observed in 12% of cases and overt bleeding was observed in 2% of cases. The hemorrhage was self-limiting and no patient required nasopharyngeal treatment [10].
- CSF leakage - Small and isolated CSF fistulas, which are treated at once successfully, are considered as minor complication in sinus surgeries [11]. These particular incidents are not rare – in a survey, 25% of American otorhinolaryngologists had experienced at least one unexpected CSF fistula intraoperatively during endoscopic sinus surgeries within 5 years [12]. The rate of unexpected dura exposure is reported with a percentage of 0.2% [8]. The number of minimal, temporary and occult leakage of cerebrospinal fluid ceasing spontaneously without clinical relevance, is significantly higher [13]. Once a small cerebrospinal fluid leak is confirmed, references recommend conservative treatment to begin with [12, 14, 15, 16]. In a few cases lumbar drainage was solely carried out [17]. However, in case of a persisting leak encountered during routine sinus surgeries or e.g. after rhino-neurosurgical procedures, surgical treatment should be pursued even with small defects.
- Orbital hematoma - The incidence of orbital hematomas is around 0.1% in all procedures [18, 19]. Visual loss and blindness have been reported but are extremely rare. Another uncommon problem is damage to the muscles that move the eye, leading to double vision, which can be temporary or permanent. In certain circumstances, there may be a change in the function of the tear ducts causing excessive tearing. Since the eye is in close proximity to the sinuses, a major orbital complication or blindness could possibly occur even without surgery for patients with severe or refractory sinus infections.
- Voice changes - One of the functions of the sinuses is to affect resonance, therefore, there is a potential change in the voice after sinus surgery.
- Impaired sense of taste or smell - The sense of smell usually improves after the procedure because airflow is restored, although in sporadic cases it could worsen depending on the extent of swelling, infection, or allergy. This impairment is often temporary but can be prolonged.
- Nasal obstruction, dryness and pain - Although preventative measures are performed by the surgeon at the time of procedure, the cartilage may move after the surgery which may rarely lead to persistent blockage. Surgery typically improves airflow, but in some patients, it may not improve or rarely may worsen. Small scar bands may also occur in the nose and require removal by the surgeon at postoperative visits. Over-aggressive resection of the turbinate structures may leave some patients with the sensation of being overly dry or even cause chronic pain.
- Adverse reactions to the topical decongestants or anesthetic provided prior to the procedure may occur. Thus, before administering these topical medications, patients' allergies should be verified

## 8.2 Definitions of Adverse Device Events and Adverse Events

### Adverse Device Effect (ADE)

- An "Adverse Device Effect" is an adverse event related to the use of an investigational medical device.
- This includes any adverse event resulting from insufficiencies or inadequacies in the instructions for use, the deployment, the implantation, the installation, the operation, or any malfunction of the investigational medical device.
- This includes any event that is a result of a use error or intentional misuse.
- "Adverse Events" are defined as any untoward medical occurrence, unintended disease or injury or any untoward clinical signs (including an abnormal laboratory finding) in subjects, users or other persons whether or not related to the investigational medical device.
- This includes events related to the investigational device.
- This includes events related to the procedures involved (any procedure in the clinical investigation plan).
- For users or other persons this is restricted to events related to the investigational medical device.
- All Adverse device effects must be recorded in the CRF. A description of the event, including the start date, resolution date, action taken, and the outcome should be provided.

All adverse events will be graded for severity as follows:

Grade	Degree	Description
1	Mild	Symptom(s) barely noticeable to patient or does not make patient uncomfortable; does not influence performance or functioning; prescription drug not ordinarily needed for relief of symptom(s) but may be given because of personality of patient.
2	Moderate	Symptom(s) of a sufficient severity to make patient uncomfortable; performance of daily activity is influenced; patient is able to continue in study; treatment for symptom(s) may be needed.
3	Severe	Cause severe discomfort; symptoms cause incapacitation or significant impact on patient's daily life; severity may cause cessation of treatment with study device; treatment for symptom(s) may be given and/or patient hospitalized.
4	Life-threatening	May result in death if not promptly treated and reversed.
5	Fatal	Results in death

**Relationship** -whether or not the test procedure/device caused the adverse event

Degree	Description
Definitely	There is evidence of exposure to the test procedure/device , the AE is most likely to be explained by the test procedure / device than by another cause; the challenge is positive; rechallenge (if feasible) is positive; the AE shows a pattern consistent with previous knowledge of the test procedure / device.

Degree	Description
Probably	There is evidence of exposure to the test procedure / device; the temporal sequence of the AE onset relative to the test procedure / device is reasonable; the AE is more likely explained by the test procedure / device than by another cause.
Possibly	There is evidence of exposure to the test procedure / device; the temporal sequence of the AE relative to the test procedure / device is reasonable; the AE could have been due to another equally likely cause;
Probably not	There is evidence of exposure to the test procedure / device; there is another more likely cause of the AE
Definitely not	The patient did not receive the test procedure / device; or temporal sequence of the AE onset relative to test procedure / device is not reasonable; or there is another obvious cause of the AE.

**Action taken** - whether or not the adverse event caused the subject to be discontinued from the study.

**Clinical Outcome** – whether the adverse event was resolved or ongoing.

All adverse events, including a worsening of physical examination findings, in comparison with baseline values, must be followed until the event resolves, the condition stabilizes, the event is otherwise explained, or the patient is lost to follow-up.

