	
4. A patient who is able to understand the requirements of the study, is willing to comply with its instructions and schedules, and agrees to sign the informed consent
 
Exclusion Criteria:
 
 
1. Known history of any significant medical disorder, which in the investigator's judgment contraindicates the patient's participation
 
2. Patients with known current or previous bleeding disorder receiving anticoagulants (e.g., chronic Coumadin treatment)
 

Study Duration	
Per Patient: between 1 day and 30 days, depending on the interval between pre-operative visit (inclusion) and day of procedure.
 
Total 10 months to recruit and treat 15 patients.

Statistical Analysis Plan	NA

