### Visit 2: Procedure and Study Termination

- **Before the procedure:**
  - Eligible subject/s will attend the Medical Center at the day of procedure and will be inquired by the PI regarding changes to their health status since the screening visit. If at this point it is determined that the patient **does not** meet all Inclusion and Exclusion criteria and cannot be treated, the patient will be exited from the study. These patients will be considered screening failures, and will not be included in any of the safety or efficacy endpoint analyses.
- **Endoscopy:**
  1. Patients may undergo BSD under local anesthesia, intravenous sedation and local anesthesia or under general anesthesia, at physician discretion.
  2. The Sinusway device will be prepared for use per its instructions for use.
  3. Evaluation of the patient with physician's typical rigid endoscope(s). Visualization of the sinuses (frontal, maxillary, sphenoid) will be recorded as performed/failed and an Image of the anatomic landmark will be taken.

4. Following the Evaluation with physician's typical rigid endoscope(s) the evaluation will be repeated using the Sinusway endoscope. Access to the sinuses (frontal, maxillary, sphenoid) will be recorded as performed/failed and an Image of the anatomic landmark will be taken. Nasal Cavity and sinuses inflammation score will be captured using the Lund Mackay CT and endoscopy score.
5. BSD procedure will be performed with either endoscope.
6. Irrigation of the nasal anatomy will be performed and recorded as Done/Not Done and which sinus was irrigated.
7. Following the BSD procedure, repeated evaluation of patient's sinuses and nasal cavity will be performed using the Sinusway endoscope
8. Usability assessment will be completed by physician.
9. If applicable, patient pain assessment using a 0-10 pain Scale and patient tolerability will be captured (Office procedures only)

- **After the procedure:**
  - The patient will recover from the procedure per physician's common practice. Before patient's release, recording of AE, if any, will be performed. Patient will exit the study.

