## 8.6 Adverse Event Reporting

It is the responsibility of the investigator to document all treatment related and device related Adverse Events (ADE's), which occur during the course of the study. All ADEs will be recorded on the adverse events page of the CRF. Severity and relationship to study device will be assigned by the investigator as described in the section above. ADEs will be recorded after the subject has been admitted to the clinic Visit-2.

Any SAE, whether deemed device-related or not, must be reported to the site Ethics Committee and to the sponsor as soon as possible after the investigator has become aware of its occurrence even if not all the information is available at the time of initial contact.

The investigator must complete a SAE Form, and send it to the Sponsor within 24 hours of becoming aware of the event. Accompanying documentation, such as copies of hospital case reports, autopsy report, and other documents when applicable, should be sent as soon as they are available.

The site's Ethics Committee must also be duly notified and dealt with, according to the Hospital and FDA/Ministry of Health regulations. Subjects who have had a SAE must be followed clinically until all parameters (including laboratory) have either returned to normal or are stabilized.

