## 9 DATA MANAGEMENT

Data from each subject will be recorded in source data and transmitted to case report forms (CRFs) supplied by the Sponsor. The data will be inserted manually and quality check for errors and omissions will be performed to ensure the accuracy of the entered data.

The source data should be completed during the study by qualified personnel. All data must be filled out using ball pens (not pencils), accurately and promptly following each relevant step of the study. The CRF should be completed in full, i.e., no fields should be left blank once the subject has completed the study. CRFs entries corrections must be made only by lining out (single line) incorrect data and writing in the revisions. All corrections must be initialed and dated by the individual performing/recording the correction. If the reason for the change is not obvious, an explanation for the change should be recorded and attached to the CRF. Blacking out or using correction fluid or an eraser is not allowed to correct or eliminate data. The investigator must review the CRFs for completeness and accuracy and must sign/date the forms where indicated.

The investigator will retain originals of CRFs, subject consent forms, and study data as permanent records for a period of 2 years or until the data is no longer required for regulatory purposes (the longest between these two).

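### Adverse events must be followed to an end-point under 8.2 and 8.6, but 6.2, Table 1 and the synopsis exit every patient at Visit 2, so the later course of an event still open at release goes uncollected if the exit rule is applied

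*Protocol*

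**What the plan says.** Two sets of rules bear on an adverse event that has been recorded but has not ended when the patient leaves.

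**Follow-up duty.** Section 8.2 states that all adverse events "must be followed until the event resolves, the condition stabilizes, the event is otherwise explained, or the patient is lost to follow-up". It applies to every event, serious or not. Section 8.6 adds, for serious events: "Subjects who have had a SAE must be followed clinically until all parameters (including laboratory) have either returned to normal or are stabilized". For each adverse device effect, section 8.2 also asks for a CRF description "including the start date, resolution date, action taken, and the outcome should be provided", and it defines clinical outcome as "whether the adverse event was resolved or ongoing".

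**Exit rule.** Section 6.2 names Visit 2 as both the procedure visit and the end of the study, and closes it with: "Before patient's release, recording of AE, if any, will be performed. Patient will exit the study". Table 1 marks adverse events and patient exit in the Visit 2 column only, and that is the last column. The synopsis gives a per-patient duration of 1 to 30 days, "depending on the interval between pre-operative visit (inclusion) and day of procedure", so participation ends with the procedure day. Section 4.1 describes device effects as collected throughout the procedure.

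**Endpoint.** Section 4.3 makes adverse device effects the primary safety endpoint, summarised by type, frequency and severity and compared descriptively with the literature.

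**The concern.** A planned exit at release is none of the four ways in which 8.2 lets follow-up end. The event has not resolved, stabilised or been explained, and a patient discharged on schedule is not lost to follow-up. A site holding an open event therefore has one instruction to keep following it and another to exit the patient, and the protocol does not say which applies. Two sites could reasonably act differently.

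At stake is the later course of events that are already on record. If the exit rule is applied, a worsening after release does not reach the CRF, so the severity grade stays at its pre-release value. The resolution date and final outcome are missing too. This is a matter of what data are collected, so no later analysis document could repair it.

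**Working it through.** There is no planned figure to reproduce: section 7 says that no statistical analysis will be used and gives no basis for the sample size. The check is mainly a comparison of the text.

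**Step 1. Rules applied to an event open at release**

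| Place | Requirement | Can it be met if the patient exits at release? |
|---|---|---|
| 8.2, follow-up | Follow every event to one of four end-points | No |
| 8.6 | Follow serious events until normal or stable | No |
| 8.2, outcome | Resolved or ongoing | Yes, as ongoing; the final state stays unknown |
| 8.2, CRF description | Resolution date | No, none exists yet |
| 4.3 | Severity of each device effect | Only as seen up to release |
| 6.2, Table 1, synopsis | Exit at Visit 2 | Yes |

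**Step 2. Is there a bridge?** Scheduled time after the procedure visit is 0 days. No section provides a contact or visit for an open event after exit, and 6.2 makes no exception for one. Release follows recovery under the physician's usual practice, so an overnight stay could move exit slightly past the procedure day. That does not remove the conflict.

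**Step 3. Scale.** Inputs: n = 15 (section 7) and a minor-complication rate of 5% (section 8.1). Assumptions: the rate carries over to this study, patients are independent, and each complication is recorded as one patient's event before release.

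- Expected patients with an event: 15 × 0.05 = 0.75.
- Probability of at least one: 1 − 0.95^15 = 1 − 0.463 = 0.537, or 54%.

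Let s be the share of these events still open at release. The protocol gives no value for s.

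- Expected patients with an open event: 0.75 × s, from 0 (s = 0) to 0.75 (s = 1).
- Probability of at least one: 1 − (1 − 0.05 × s)^15, from 0% to 54%.

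For the major-complication rate of 0.5–1% in the same section, the expected count is 15 × 0.005 = 0.075 to 15 × 0.01 = 0.15. The probability of at least one is 7.2% to 14.0%, again before applying an unknown share open at release. One patient is 1/15 = 6.7% of the study.

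**The case against.** The strongest reply is that this is a missing mechanism and not a contradiction. On that view 6.2, Table 1 and the synopsis give the default schedule, while 8.2 and 8.6 are event-driven duties that may run past it. This reading is possible, and under it nothing is lost. But the protocol does not state it: 6.2 exits the patient without exception, and no contact is provided to carry out the duty. The need to reconcile the sections stands on either reading.

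Several stronger readings are tempting, and the document does not support them.

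- *The CRF cannot be completed.* Section 9 says that "no fields should be left blank once the subject has completed the study", and a reader might infer an impossible form. Ongoing is a valid outcome entry, so the outcome field need not be blank. Only the resolution date cannot be supplied.
- *About two patients will be affected.* Section 8.1 reports 12% oozing and 2% overt bleeding in a transnasal endoscopy series, and 15 × 0.14 = 2.1. But that series concerns a different procedure and was assessed when the procedure ended, and its bleeding was self-limiting. An event that is stable at release has also already met an 8.2 end-point. The figure says nothing about events open at release.
- *Severity will be understated against the literature.* This is not shown. The bleeding series was graded at about the time Visit 2 would grade.
- *Grades 2 and 3 cannot be assigned before release.* They mention daily activity or daily life, but also discomfort, incapacitation and need for treatment, which can be seen on site.
- *The outcome codes are inadequate.* A stabilised event fits under ongoing, and death is captured as grade 5. A longer code list is a preference.

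It is also fair to say that 4.3 lists severity and not outcome. A missing outcome alone leaves the primary endpoint unchanged; only an uncaptured worsening would alter it.

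**Conclusion.** The point holds as a conflict in the current text between the follow-up duty in 8.2 and 8.6 and the exit rule in 6.2, Table 1 and the synopsis. Its effect is conditional. If sites apply the exit rule, later worsening, the resolution date and the final outcome of an open event are not captured, and the worsening would have changed a component of the primary endpoint. If sites apply 8.2, the data could be collected, but through no route that the protocol describes.

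The number of patients affected cannot be computed. At the 5% minor-complication rate it lies between 0 and 0.75 expected patients of 15, depending wholly on a share that the protocol does not give. The conflict does not depend on that number. In a small, uncontrolled study with safety as its primary endpoint, it should be settled before enrolment.

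**What to change.** Reconcile 6.2, Table 1 and the synopsis with 8.2 and 8.6 by making study exit conditional:

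- In 6.2, a subject with no open event exits at release as now. A subject with an adverse event or serious adverse event open at release stays in the study for safety follow-up until one of the 8.2 end-points is reached.
- In Table 1, add a conditional entry for follow-up of open adverse events after Visit 2.
- In the synopsis, state that the per-patient duration can run past the procedure day for these subjects.
- In 8.2 or 8.6, say that the recorded severity is updated if the event worsens, and that the resolution date and outcome are completed when follow-up ends.

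The cost is protocol wording, a contact for the few subjects with an open event, and a longer participation for them. All other subjects keep the present two-visit schedule.

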#### Anticipated adverse events

Anticipated adverse device effects include Infection, Excessive Bleeding, Nasomucosal injury, CSF leakage, Orbital hematoma, Voice changes, Impaired sense of taste or smell, Nasal obstruction, dryness and pain and Adverse reactions to the topical decongestants or anesthetic provided prior to the procedure. Please refer to section 8.1 above

### 8.3 Definitions of Serious Adverse Device Effects and device deficiencies

#### Serious Adverse Device Effect (SADE)

A "Serious Adverse Device Effect" is an adverse device effect that has resulted in any of the consequences characteristic of a serious adverse event.

#### Serious Adverse Event (SAE)

A "Serious Adverse Event" is an adverse event that:

- led to a death (Note: In the event of subject death during the conduct of the study, efforts should be made to perform an autopsy.)
- led to a serious deterioration in health that either:

- 1) resulted in a life-threatening illness or injury, or
- 2) resulted in a permanent impairment of a body structure or a body function, or
- 3) required in-patient hospitalization or prolongation of existing hospitalization, or
- 4) resulted in medical or surgical intervention to prevent life threatening illness or injury or permanent impairment to a body structure or a body function

c) led to fetal distress, fetal death or a congenital abnormality or birth defect.

- This includes device deficiencies that might have led to a serious adverse event if a) suitable action had not been taken or b) intervention had not been made or c) if circumstances had been less fortunate. These are handled under the SAE reporting system.
- A planned hospitalization for pre-existing condition, or a procedure required by the Clinical Investigation Plan, without a serious deterioration in health, is not considered to be a serious adverse event.

